1539 statistical approach. The DSMC will be responsible for monitoring the SCORE Study
1540 following the scientific plan only.

1541

1542 **6.2 Formal Regulatory Statistical Test of Efficacy**

1543 For regulatory purposes, the SCORE Study will be configured as two separate and
1544 independent clinical trials “A” and “B”, each trial to serve as confirmatory of the other. To
1545 accomplish this, clinical sites will be allocated before recruitment commences to either trial
1546 “A” or trial “B”, using a method that strives for comparable geographic patterns and
1547 distributions of enrollees per center. Within each trial, CRVO and BRVO disease areas
1548 will be pooled for analysis and three primary efficacy analyses performed after no more
1549 than one year of follow-up. A detailed description of the method of assigning sites to Trial
1550 “A” and Trial “B” is provided in the SCORE Study Manual of Procedures and Policies
1551 (MOPP). The assignment of sites to Trial “A” and Trial “B” will be made prior to
1552 recruitment of subjects. One analysis will compare 1 mg steroid versus standard care, one
1553 will compare 4 mg steroid versus standard care, and one will compare 1 mg versus 4 mg
1554 steroid. The comparison will be with respect to the primary outcome measure. The
1555 primary outcome measure indicates whether or not a study eye of a participant experiences
1556 an improvement of 15 or more letters from baseline in best-corrected ETDRS visual acuity
1557 score. The significance of the three comparisons will be obtained by Hochberg’s
1558 sequentially rejective procedure, as described in detail in the MOPP, section 6.2. The
1559 overall alpha for the A trial will be no more than 0.05, and similarly for the independent B
1560 trial (more specifically, the alpha for each of the “A” and “B” trials will be diminished from
1561 0.05 by the amount of alpha previously spent on interim scientific efficacy assessments).
1562 Within trial “A” and within trial “B”, an initial analysis of treatment effect will be carried
1563 out by logistic regression to determine whether a statistical interaction exists between
1564 disease group (BRVO and CRVO) and treatment group (standard care, 4 mg steroid, and 1

1565 mg steroid). A finding of no interaction effect will provide justification for pooling the
1566 CRVO and BRVO participants within trial "A" and trial "B" and the primary efficacy

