1567 analyses for regulatory purposes, as described above, will be carried out by means of
1568 logistic regression adjusting for disease area, baseline visual acuity, and center. A
1569 statistically significant interaction effect will require separate primary efficacy analyses for
1570 CRVO and for BRVO within trial "A" and with trial "B".

1571

1572 **6.3 Scientific Statistical Approach**

1573 **6.3.1 Two Independent Clinical Trials**

1574 The SCORE Study consists of two separate independent clinical trials - one for
1575 CRVO and one for BRVO. Each of these clinical trials has its own overall Type I
1576 error (alpha) = .05.

1577

1578 **6.3.2 Three Primary Questions in Each Clinical Trial**

1579 Each of these clinical trials asks three questions. One question is the comparison of
1580 standard care to 4 mg intravitreal injection(s) of triamcinolone acetonide. A second
1581 question is the comparison of standard care to 1 mg intravitreal injection(s) of
1582 triamcinolone acetonide. The third question compares 1 mg to 4 mg intravitreal
1583 injections. Within each clinical trial, the significance of the comparisons will be
1584 obtained by Hochberg's sequentially rejective procedure using an alpha level of 0.05
1585 (see the MOPP, section 6.4).

1586 **6.3.3 Primary Efficacy Outcome Measure and Time Point**

1587 Improvement by 15 or more letters from the randomization visit visual acuity to the
1588 12-month follow-up visual acuity is the primary efficacy outcome measure. Visual
1589 acuity is to be measured using E-ETDRS visual acuity testing.

1590

1591 **6.3.3.1 Primary Efficacy Analysis Method**

1592 The three treatment comparisons (1 mg versus standard care, 4 mg versus
1593 standard care, and 1 mg versus 4 mg) will be made by means of logistic
1594 regression adjusting for baseline visual acuity, clinical site, and presence of
1595 baseline macular hemorrhage in participants with BRVO. The test statistic

1596 will be compared to the critical value of the efficacy monitoring guideline
1597 (section 6.7.2). Family-wise error will be controlled at no more than 0.05 by
1598 Hochberg's sequentially rejective method, modified for interim monitoring as
1599 specified in the MOPP.

1600

1601 The analysis will be on the basis of intent to treat (ITT), treating missing
1602 observations as missing completely at random [i.e., missing data from study
1603 participants will be dropped from the analysis and noncompliance (or

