6.3.3.2 Additional Analysis Methods for Consistency of Primary Efficacy Result

We will investigate two other ITT variants: (1) last-observation-carried-forward (LOCF) and (2) performing a sensitivity analysis in which outcomes will be assigned to missing eyes so as to explore both the minimum and maximum possible estimates of treatment effects. A per-protocol analysis, excluded from which will be those study participants who drop out, cross over to another treatment group, or violate the protocol, also will be conducted including only study eyes that have completed 12-month visual acuity data. Logistic regression analysis will be performed to adjust for any potential imbalances in baseline characteristics observed between treatment groups, with the odds ratio used as a measure of increased or decreased risk.

1626 **6.4 Assumptions for and Result of Sample Size Estimation**1627 **6.4.1 Study Power**

1628 The study power is set for each trial at 80%.

1629

1630 **6.4.2 Estimate of CRVO Primary Efficacy Outcome in the Standard Care Group**1631 The Central Vein Occlusion Study (CVOS) demonstrated that in participants with
1632 macular edema for more than 3 months secondary to a CRVO, macular grid laser
1633 photocoagulation, as compared to no treatment, did not improve visual acuity.⁴ There
1634 were no significant differences between treated and untreated participants in either
1635 level of visual acuity or change in visual acuity across all follow-up visits. The data
1636 from the CVOS demonstrate that at 2 years from baseline 18% of treated eyes (10 of
1637 57 eyes) and 11% of untreated eyes (6 of 53 eyes) experienced a gain of three or more
1638 lines of visual acuity. At 1 year, approximately 6% in both the treated and untreated
1639 eyes showed a gain of three or more lines of visual acuity. From these data, it is
1640 conservatively estimated that approximately 15% of untreated eyes with CRVO will
1641 experience a gain of three or more lines of visual acuity at 1 year.

1642

1643 **6.4.3 Estimate of BRVO Primary Efficacy Outcome in the Standard Care Group**1644 In the Branch Vein Occlusion Study (BVOS), macular grid laser photocoagulation
1645 was demonstrated to be effective in improving visual acuity in some eyes with BRVO
1646 complicated by macular edema.¹ Treatment resulted in a two or more line
1647 improvement in visual acuity for two or more consecutive visits in approximately

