6.4.5 Sample Size Estimate

1698 The sample size estimate (number per group) was computed assuming the efficacy in
1699 the two steroid doses are the same. If the efficacy in the 4 mg group is higher than the
1700 1 mg group, and given the other preceding assumptions, the study power will be
1701 higher for the standard care versus 4 mg comparison. This was considered important
1702 because the 4 mg dose is the basis for all available information.

1703

Sample Size Estimate

Type I error (alpha) = .025, study power = 80%

	CRVO	BRVO
--	------	------

Standard care	15%	35%
---------------	-----	-----

1 mg or 4 mg	30%	53%
--------------	-----	-----

N per group	147	147
-------------	-----	-----

The allocation ratio will be 1:1:1 for standard care: 1 mg: 4 mg. The number per group has been increased by 10% to allow for some missing data at 12 months (number per group=162). Thus, the total sample estimate for the CRVO trial is 486 (3 times 162) and for the BRVO trial the total sample estimate is 486 (3 times 162).

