- 1749 • Change between baseline and each efficacy outcome assessment visit in best-
 1750 corrected ETDRS visual acuity score (e.g., mean change from baseline in visual
 1751 acuity, distribution of change from baseline in visual acuity based on clinically
 1752 meaningful cut points of improvement or worsening of visual acuity).
- 1753 • Change in calculated retinal thickening as assessed by optical coherence
 1754 tomography.
- 1755 • Change in retinal thickness at the center of the macula as assessed by stereoscopic
 1756 color fundus photography.
- 1757 • Change in area of retinal thickening as assessed by stereoscopic color fundus
 1758 photography.

1759

1760 **6.7 Statistical Guidelines for Interim Monitoring by the DSMC**1761 **6.7.1 Interim Monitoring for Safety**

1762 The SCORE Study will use repeated confidence intervals to continuously monitor the
1763 safety indicator variables mentioned in section 6.5. Safety rates will be reported
1764 separately in the two disease areas, but injection arms will be pooled to increase
1765 accuracy of the estimates.

1766

1767 **6.7.2 Interim Monitoring for Efficacy**

1768 The primary efficacy outcome occurs at 12 months from the randomization visit. The
1769 recruitment pattern is unpredictable. Information concerning the primary outcome
1770 will accrue as participants complete their 12-month visit and thus "information time"
1771 is the percent of the 486 patients in each trial expected to have completed this visit.

1772

1773 Of the Type I error (α) = .05 for each trial, α = 0.005 will be allocated for
1774 interim monitoring and the remaining α = 0.045 will be reserved for the final
1775 analysis. With α = 0.045 for the final analysis, the estimate of the sample size
1776 does not need to be increased for interim monitoring. Interim testing will be carried
1777 out using the Lan-DeMets interim monitoring boundary with an O'Brien-Fleming-
1778 type spending function where at most 0.005 cumulative α can be spent prior to the
1779 final analysis. The "height of the hurdle" is highest when the information fraction is
1780 smallest and decreases as additional patients complete 12 months. The "height of the
1781 hurdle" can be calculated for each DSMC meeting based on the number of patients
1782 expected to have completed the 12-month visit and the α spent by previous
1783 "looks" by the DSMC. With the specification that the total α for interim

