1784 monitoring is 0.005, the maximum amount the DSMC can "spend" is 0.005. If the
1785 DSMC looks more often, it will "spend" less per look.

1786

1787 Formally, if t is the information fraction, $B(t)$ is the 2-sided cumulative O'Brien-
1788 Fleming-type spending function of Lan & DeMets with final value $B(1) = 0.005$, and
1789 $S(t)$ is the two-sided cumulative spending function used by SCORE, then

$$1790 S(t) = \begin{cases} B(t) & \text{for } 0 \leq t < 1 \\ 0.05 & \text{for } t = 1 \end{cases}$$

1791
1792 At each interim inspection, the three comparisons will be made using the Lan-DeMets
1793 methodology, and the results combined using Hochberg's sequentially rejective
1794 procedure as described in the MOPP, section 6.4.

1795 **6.7.3 Interim Monitoring for Futility**

1796 The DSMC will consider futility as well as safety and efficacy. One method of
1797 statistically assessing futility is to use conditional power to estimate the likelihood of
1798 statistical significance given the observed efficacy results and various possible
1799 choices for the remaining results.

1800

1801 **6.7.4 Analyses and Results Requested to be Considered Prior to** 1802 **Recommending Early Termination**

1803
1804 Before recommending early termination, the DSMC will consider:

- 1805 • internal consistency of primary and secondary results
- 1806 • internal consistency of primary and secondary results by subgroups
1807 defined by baseline characteristics (e.g. visual acuity categories, categories
1808 based on length of history of CRVO or BRVO, and time period of
1809 enrollment)
- 1810 • distribution of baseline prognostic factors among the three groups
1811 (standard care, 4 mg, 1 mg)
- 1812 • consistency of primary and secondary results across clinical centers and
1813 among centers enrolling larger numbers of patients

1814 • possible bias in assessment of primary and secondary response variables,
1815 particularly visual acuity, given the unmasked implementation of standard
1816 care versus intravitreal triamcinolone
1817 • possible impact of missing data from missed patient visits for assessment
1818 of the primary and secondary response variables
1819 • possible differences in concomitant interventions or medications.

1820 **6.7.5 Study Timeline and DSMC Data Reviews**

1821 The DSMC will meet to review study data starting in November 2004, and every 6
1822 months until 3-year follow-up is concluded on all study participants. Table 6 depicts

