1823 the fractions of the population enrolled, with 1 year follow-up, and with 3 year
1824 follow-up, assuming that enrollment is constant, starts in August 2004, and takes 18
1825 months. Under this assumption, there will be 10 DSMC meetings. Formal interim
1826 inspection for 1-year efficacy will take place only during the four meetings when the
1827 information fraction is nonzero, that is, in November and May of 2005 and 2006.

1828 **Table 6: Study Timeline for DSMC Data Reviews**

1829 Date of DSMC Meeting	1830 Fraction		
	1831 Enrolled	1832 With 1-year 1833 follow-up	1834 With 3-year 1835 follow-up
November 2004	2/9		
May 2005	5/9		
November 2005	8/9	2/9	
May 2006	1	5/9	
November 2006		8/9	
May 2007		1	
November 2007			2/9
May 2008			5/9
November 2008			8/9
May 2009			1

1832 7. Confidentiality and Access to Source Data / Documents

1833 The investigators will maintain the highest degree of confidentiality permitted for the clinical and
1834 research information obtained from participants in this clinical study. Medical and research
1835 records should be maintained in the strictest confidence. However, as part of the quality
1836 assurance and legal responsibilities of an investigator, the site must permit authorized
1837 representatives of the sponsor(s), the SCORE Coordinating Center, and regulatory agencies to
1838 examine (and when permitted or required by applicable law, to copy) clinical records for the
1839 purposes of quality assurance reviews, audits and evaluation of the study safety and progress.
1840 Unless required by the law, no copying of records with personally identifying information will be
1841 permitted. Only the coded identity associated with documents or other participant data may be
1842 copied (obscuring any personally identifying information) or transmitted to the SCORE
1843 Coordinating Center. Authorized representatives as noted above are bound to maintain the strict
1844 confidentiality of medical and research information that may be linked to identified individuals.
1845 The site will normally be notified in advance of monitoring and auditing visits.

1846

1847 8. Summary of Good Clinical Practice Compliance

1848 This trial will be conducted in accordance with Good Clinical Practice (GCP) using the guidance
1849 documents and practices offered by ICH and FDA, and in accordance with the Declarations of
1850 Helsinki and the policies and procedures for the SCORE Coordinating Center at The EMMES

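### Hochberg is valid and delivers about the planned 80% per dose, but with three arms a closed Simes test would give about 84% per dose and 78-79% instead of 70-71% for both doses, at the price of Hochberg's spare error margin

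*Combined protocol and SAP*

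**What the plan says.** Each disease trial asks three questions: 4 mg against standard care, 1 mg against standard care, and 1 mg against 4 mg. Section 6.3.2 judges them by Hochberg's "sequentially rejective procedure using an alpha level of 0.05". Section 6.3.3.1 repeats this ("Family-wise error will be controlled at no more than 0.05 by" Hochberg's method, modified for interim looks as set out in the MOPP) and names logistic regression adjusted for baseline acuity, clinical site and, in BRVO, macular hemorrhage. Section 6.7.2 applies the same rule during monitoring: "At each interim inspection, the three comparisons will be made using the Lan-DeMets" method, with the results combined by Hochberg.

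On the final level, 6.7.2 says that "0.045 will be reserved for the final" analysis, but its spending function ends at S(1) = 0.05.

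On size, 6.4.1 sets 80% power for each trial. The calculation in 6.4.5 uses alpha .025 and gives 147 per group: "The sample size estimate (number per group) was computed assuming the efficacy in" the two doses is the same. No target is set for showing that both doses work.

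**The concern.** The plan assumes equal efficacy for the two doses, so the 1 mg v 4 mg p-value will usually be large. Hochberg allows the full level only when all three p-values are at or below it. In practice, then, each dose has to beat standard care at about alpha/2.

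With three arms that restriction is stricter than family-wise control requires. If two of the pairwise equalities are true, the third is true as well. The only joint hypothesis that needs protection is therefore equality of all three arms. Once that is rejected, at most one pairwise equality can be true, and each comparison can be tested at the full level.

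At stake is the chance of missing one of two effective doses. Section 2.5 includes 1 mg for its potential for lower risk, so a separate answer for each dose has value.

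**Working it through.** **Inputs.** Rates from 6.4.5: CRVO 15% under standard care and 30% on each dose; BRVO 35% and 53%. Evaluable N is 147 per arm, allocation 1:1:1. Tests are two-sided, as S(t) in 6.7.2 is.

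**The plan's own N.** With z(0.0125) = 2.2414, z(0.20) = 0.8416 and m the mean of the two rates:

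n = [2.2414·√(2m(1−m)) + 0.8416·√(p₀(1−p₀) + p₁(1−p₁))]² / (p₁−p₀)²

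- CRVO: [2.2414·√0.34875 + 0.8416·√0.3375]² / 0.0225 = 146.02, so 147, as stated.
- BRVO: [2.2414·√0.4928 + 0.8416·√0.4766]² / 0.0324 = 143.3, so 144. The plan states 147, within 3%.

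**The two rules**, with ordered p-values p(1) ≤ p(2) ≤ p(3) and level a:

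- Hochberg: if p(3) ≤ a, reject all three; otherwise, if p(2) ≤ a/2, reject the two smallest; otherwise, if p(1) ≤ a/3, reject the smallest.
- Closed Simes: if p(1) ≤ a/3, or p(2) ≤ 2a/3, or p(3) ≤ a, reject equality of all three arms and declare every comparison with p ≤ a; otherwise declare none.

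Each Hochberg condition satisfies the Simes condition (a/2 is below 2a/3), and every p-value that Hochberg rejects is at most a. No Hochberg rejection at the same level can be lost. The difference shows when, at a = 0.05, one dose has p ≤ 0.0167, the other has p between 0.025 and 0.05, and the 1 mg v 4 mg p-value exceeds 0.05. Hochberg then declares only the first dose; closed Simes declares both.

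**Power.** Exact enumeration over all three-arm outcomes, 147 per arm, unadjusted pooled z-tests, Hochberg → closed Simes:

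| Level | Trial | Per dose | Both doses | At least one |
|---|---|---|---|---|
| 0.05 | CRVO | 79.9 → 84.2% | 70.4 → 78.4% | 89.4 → 90.0% |
| 0.05 | BRVO | 80.1 → 84.4% | 70.9 → 79.0% | 89.3 → 89.8% |
| 0.045 | CRVO | 78.7 → 82.9% | 68.9 → 76.8% | 88.6 → 89.1% |
| 0.045 | BRVO | 79.1 → 83.6% | 68.9 → 77.5% | 89.2 → 89.7% |

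No rejection was lost in any scenario.

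**False claims at 0.05, same method:**

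| Situation | CRVO | BRVO |
|---|---|---|
| 1 mg v 4 mg, both doses equally effective | 3.9 → 5.0% | 4.0 → 5.3% |
| Inert dose v standard care, other dose works | 4.0 → 5.1% | 4.0 → 5.0% |
| All arms equal, any false claim | 4.3 → 4.5% | 4.5 → 4.7% |
| All arms equal, both doses declared different from standard care | 0.37 → 0.73% | 0.37 → 0.73% |

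The BRVO 5.3% reflects the discreteness of the z-test; normal theory gives 4.95%. Two-sided pairwise statistics do not meet the usual dependence condition for Simes, so validity when all arms are equal rests on the computed error: 4.5-4.7% here and 4.6% with Gaussian data.

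**Interim looks.** With looks at 2/9, 5/9, 8/9 and 1 (the one-year fractions in Table 6) and S(t), normal-theory simulation of 1,000,000 trials gives closed Simes 4.70% when all arms are equal, 4.96% for a false 1 mg v 4 mg claim and 4.94% for an inert dose.

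**Site-adjusted model.** The plan adjusts for site but gives no number of sites, so the counts below are assumed. Wald tests with fixed site effects, CRVO rates, 20,000 trials each, false 1 mg v 4 mg claim:

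| Sites (assumed) | Hochberg → closed Simes |
|---|---|
| 10 | 4.1 → 5.3% |
| 30 | 4.5 → 5.8% |
| 60 | 5.3 → 6.7% |

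This inflation comes from the Wald test with many site terms, not from closure. Hochberg's margin absorbs part of it; closed Simes does not.

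**The case against.** The strongest objection is that nothing is broken. The plan's only power target is 80%, and Hochberg meets it to within rounding at 0.05. The larger gain is for winning on both doses, for which no target exists, and the chance of showing that at least one dose works hardly moves. That stands: this is an improvement on offer, and the plan can be run without it.

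A second objection concerns the error cost. A reader might infer that a single false claim rises only to the nominal 5%. The documents do not support that for the planned analysis: with site-adjusted Wald tests it can go above 5%, and at 30 assumed sites Hochberg stays below 5% where closed Simes does not. This also stands, and the fix has to deal with it.

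Third, the MOPP's interim version of Hochberg is not among the documents. The comparison is with plain Hochberg, and the MOPP may already use this closure.

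Fourth, the change would come late. Section 4.8 dates version 7.0 to February 2008, and 6.7.5 plans formal efficacy looks in 2005 and 2006, "assuming that enrollment is constant, starts in August 2004, and takes 18" months. Loosening the primary multiplicity rule at that stage invites challenge unless those who make the change have had no access to comparative results.

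Last, a reader might carry the change over to 6.2, which also uses Hochberg ("The significance of the three comparisons will be obtained by" that procedure). The documents give no sizes for trials A and B, so no gain can be shown there.

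**Conclusion.** The point holds as a cheap improvement, not as a defect. Hochberg controls the error rate and delivers about the stated 80% per dose. A reader might infer from the both-doses figure of 70-71% that the trial is underpowered; the documents set no such target, so that does not follow.

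Under the plan's rates, 147 evaluable per arm and unadjusted tests, closed Simes adds about 4 points of power per dose and about 8 points for both doses, with a similar gain at 0.045. In exchange Hochberg's margin is used up. The rise in a single false claim from about 4% to about 5% applies when the other two comparisons have the design effect and the p-values are well calibrated. When all arms are equal, family-wise error stays at or below 4.7%.

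The algebra and the unadjusted figures are firm. The benefit over the rule actually in the MOPP cannot be checked, and the site-adjusted error rates depend on assumed site counts.

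**What to change.** In 6.3.3.1, with matching wording in 6.3.2 and 6.7.2, replace Hochberg by:

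*Order the three p-values p(1) ≤ p(2) ≤ p(3). Reject equality of all three arms if p(1) ≤ a/3, or p(2) ≤ 2a/3, or p(3) ≤ a. If it is rejected, declare every comparison with p ≤ a; otherwise declare none. At each inspection, a is that look's two-sided nominal level under 6.7.2.*

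In the same edit:

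- State whether the final level is 0.045 or 0.05, since 6.7.2 supports both.
- Take the p-values from a test that holds its size with many sites, such as a score test or a site-stratified (conditional) test, in place of Wald tests with fixed site terms.
- Date the change before the final 12-month comparison is unmasked, and have it made by people without access to comparative results.
- If the MOPP already uses this closure, say so in the protocol instead.

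Leave 6.2, N = 147 and the 80% statement unchanged. The change needs no added patients, visits or data, only wording here and in the matching MOPP section. The statistical price is the loss of Hochberg's margin, as shown in the working.
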